PROTOCOL TITLE

Neuromodulation of placebo and nocebo effects

IDENTIFIER

NCT03102710

DATE

4/30/2019

SPECIFIC AIMS

Specific Aim 1: Characterize the effect of applying tDCS to the rDLPFC to modulate placebo and nocebo effects in healthy subjects

Hypothesis 1.1: In the sham tDCS group, placebo lidocaine and capsaicin will produce a significant pain rating decrease (placebo) and increase (nocebo) respectively, in response to identical heat pain stimuli as compared to a within-subject control “neutral” cream. Both effects will be augmented by tDCS enhancement of rDLPFC excitability and blunted by tDCS inhibition of rDLPFC excitability.

Hypothesis 1.2 In the sham tDCS group, placebo treatment will produce fMRI signal increases in regions associated with the DPMS including the DLPFC, orbital prefrontal cortex (OPFC), rostral anterior cingulate cortex (rACC), periaqueductal gray (PAG), and fMRI signal decreases in pain intensity sensitive regions (insula and secondary somatosensory cortex, S2), as compared to the within-subject control in response to identical pain stimuli. These changes will increase in the tDCS enhancement cohort and blunt in the inhibition cohort.

Hypothesis 1.3 In the sham tDCS group, nocebo treatment will produce fMRI signal increases in brain regions associated with cognition and anxiety, including DLPFC, hippocampus, and OPFC, along with fMRI signal decreases in the areas associated with the affective component of pain (dorsal anterior cingulated cortex (dACC) and insula), as compared to the within-subject control neutral cream. These fMRI signal changes will be blunted in the tDCS inhibition group and increased in the tDCS enhancement group.

Specific Aim 2: Characterize how tDCS to rDLPFC can modulate functional connectivity of rDLPFC

Hypothesis 2: Enhancing rDLPFC excitability will increase resting state functional connectivity (rsFC) between the rDLPFC and rACC and insula whereas inhibiting rDLPFC excitability will decrease rsFC between the rDLPFC and rACC and insula as compared with sham tDCS. The rsFC between rDLPFC and rACC will be associated with placebo effect as indicated by pain rating difference.

STUDY PROCEDURES

We will recruit healthy subjects for this study. Please see the [Protection of Human Subjects](#) section for detailed entry criteria for screening and recruitment. In this experiment, subjects will be randomly assigned to three groups (26 per group): 1) tDCS enhancement group to increase the excitability of rDLPFC, 2) tDCS inhibition group to decrease the excitability of rDLPFC, and 3) sham tDCS group.

Subjects will participate in five experimental sessions: a training and familiarity session, contextual learning/expectancy boost session, two tDCS sessions, and a session combining tDCS and testing for placebo/nocebo effects. Sessions 1 and 2 will be separated by 2-5 days, sessions 2 and 3 will be separated by 1-5 days, then sessions 3, 4, and 5 will be applied on consecutive three days. We will measure tDCS effects via changes in subjective pain ratings, fMRI signals in response to calibrated heat pain and the rsFC.

Detailed experimental procedure

Noxious heat stimuli will be delivered using a PATHWAY system (Medoc Advanced Medical Systems). All stimuli will be initiated from a baseline temperature of 32 °C and increased to a target temperature. Each stimulus will be presented for 12 seconds, including 2.5 seconds to ramp up to the target temperature and 2.5 seconds to ramp down to baseline again. Heat stimuli will be applied to the right volar forearm. **In sessions where tDCS is applied we will administer the tDCS sensation questionnaire to ensure subjects did not have any unexpected adverse reactions.**

Randomization Subjects will be randomized into one of three groups using a centrally generated variable-sized block design: tDCS enhancement, tDCS inhibition, and sham tDCS groups.

Session 1 is a training, familiarity, and calibration session. Subjects will be trained to use the Sensory Gracely Scale (0-20) [1, 2] to rate pain experiences using the same method as in our previous studies [3, 4]. Subjects will first receive an ascending heat stimulus sequence (starting from 38 degrees). The three temperatures that each subject rates as approximately 5-6 (mild pain), 10-11 (moderate pain) and 14-15 (strong pain) will be selected. Subjects will receive a urine drug test on this day to determine no substance abuse.

Session 2 is an expectancy manipulation session [3-5]. At the beginning of the session, all subjects will be informed that the aim of this study is to use a neuromodulation tool (tDCS) to investigate the analgesic effects of lidocaine cream and the hyperalgesic effects of capsaicin cream using a neutral cream as a control. We will first apply sham tDCS for 20 minutes, and then apply all 3 creams to different spots on participants' right volar forearm. Subjects will be told that the creams will need about 20 minutes to take effect and that the effect will last for more than two hours. In reality, only sham tDCS will be applied, and an inert cream will be used for all 3

creams. The cream will be a fragrance-free moisturizing lotion dyed three different colors (blue for “Lidocaine,” pink for “Capsaicin,” and white for neutral).

After this scripted explanation, 9 unique regions of the subject's arm will be demarcated for each stimulus. We will draw a 3x3 grid comprised of 2 cm x 2 cm squares on the subject's right volar forearm, starting the grid at the subject's elbow crease. (If the volar portion of the arm is not wide enough to accommodate the 6 cm width required, we will draw one 1x3 column on the radial, lateral portion of the forearm.) The creams will then be applied with each cream spread onto a unique set of 3 adjacent squares (i.e. one cream for each row). The row placement of the neutral control cream, placebo Lidocaine and Capsaicin creams will be randomized between subjects.

Using methods similar to those of previous studies [5, 6], subjects will then be told that to test the hyperalgesia effect of capsaicin and the analgesia effect of the lidocaine, 6 identical pain stimuli will be applied to each of the nine spots. However, in reality, to boost subjects' expectancy, 6 *moderate* stimuli will be given to each of the neutral control cream spots, 6 *mild* stimuli will be applied on placebo Lidocaine cream spots, and 6 *high* stimuli will be applied on nocebo Capsaicin cream spots. The location of the placebo, nocebo and control rows will be randomized across subjects to balance the experimental design. Subjects will be asked to rate their expectancy of both the analgesic effect of lidocaine cream and the hyperalgesic effect of capsaicin using a 0-10 scale (with 0 indicating a very negative expectation of “does not work at all” and 10 indicating a very positive expectation of “very effective”) before the pain stimulus is applied and again how much they expected the cream reduced or enhanced their pain afterward. The Gracely Sensory and Affective Scale will be used to rate experienced pain during the stimulation afterward.

Session 3 is the first tDCS session. Right before and after tDCS, resting state fMRI data will be collected.

Session 4 is the second tDCS session with no fMRI scan involved.

Session 5 is the third tDCS and placebo / nocebo test session. At the beginning of the Session, subjects will be told that the Session 2 procedure will be repeated in the fMRI scanner. As in Session 2, the 3 different creams (in reality all one inert cream) will be administered to each row of squares, with “lidocaine” and “capsaicin” cream administered to the same rows as determined in Session 2. Then, tDCS will be applied based on subjects' randomization. The resting state fMRI data will be collected before and after tDCS.

After that, calibrated pain will be applied during the fMRI scan. Since this session will test the placebo/nocebo effect, we will only administer different heat stimuli to the 3 regions in the most lateral column of the 9 x 9 grid. Then, subjects will be asked to rate their expectancy of both the analgesia effect of lidocaine cream and the hyperalgesic effect of capsaicin using a 0-10 scale. After that, we will administer the same moderate stimulus to all remaining regions with all 3 creams. Our outcome measurement will be the subjective pain ratings and fMRI signal changes to identical calibrated heat pain.

At the end of the experiment, subjects will be debriefed by a licensed physician or by the Principal Investigator, [name]. We will inform them that in this study, only inert cream and sham tDCS (in session 2 or in sham tDCS group) was used, and that we changed the heat pain temperature at session 2. We will also emphasize that the experience of this study should not influence their impression of lidocaine / capsaicin or their interest in choosing these drugs as a potential therapeutic method.

Transcranial direct current stimulation (tDCS) administration

Twenty minutes of tDCS at 2mA will be applied by the StarStim system. For the rDLPFC excitability inhibition group, the cathodal electrode will be placed over F4 and the anodal electrode above the left orbit. For the rDLPFC excitability enhancement group, the anodal electrode will be placed over F4 and the cathodal electrode above the left orbit. Stimulation will start and finish with a 15 second gradual current ramp up and ramp down to decrease subjects' discomfort. For sham tDCS treatment, stimulation will be applied only at ramp periods at the beginning and end of sham stimulation to mimic the somatosensory effect of real tDCS for 15 s. As in a previous study [7], the electrodes will be placed at the same positions for the real tDCS (half rDLPFC enhancement position, half rDLPFC inhibition position).

fMRI data acquisition

The MRI scan will be performed using a 3 Tesla Siemens MRI System equipped for Echo Planar Imaging using a 32 channel head coil. fMRI data will be acquired using gradient echo T2*-weighted sequence (TR/TE=2000/30 msec, flip angle=90°, slice thickness=3 mm). The scans will include pre-tDCS resting state (8 minutes) and post-tDCS resting state (8 minutes) scans during the application of heat pain stimuli to different spots. For pain stimuli at each spot, a paradigm used in our previous study [8] will be applied, which include

anticipation, pain and pain rating, each pain sequence at one spot lasts about 5 minutes (**Figure 6**). A high-resolution 3D MPRAGE sequence with 1 mm³ isotropic resolution will also be collected for anatomic localization of the fMRI signal changes. tDCS (20 minutes) will be applied in the scanner as our tDCS device is MRI compatible.

Reference

1. Gracely, R.H., P.A. McGrath, and R. Dubner, *Ratio scales of sensory and affective verbal pain descriptors*. Pain, 1978. **5**: p. 5-18.

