PROTOCOL TITLE

Neuromodulation of placebo and nocebo effects

IDENTIFIER

NCT03102710

DATE

4/30/2019

BIOSTATISTICAL ANALYSIS

Specific Aim 1: Characterize the neural mechanisms by which tDCS to rDLPFC modulates placebo / nocebo responses in healthy subjects in an acute pain paradigm.

Primary outcome: 1) fMRI signal changes evoked by identical experimental pain in different conditions (before and after different inert creams) after different tDCS interventions; 2) placebo and nocebo effect difference (as indicated by pain rating differences) after different tDCS interventions.

Similar to our previous studies [1-3], fMRI data processing and statistical analyses will be carried out using SPM8 (<http://www.fil.ion.ucl.ac.uk/spm/>). Preprocessing will include co-registration, motion correction, normalization to MNI stereotactic space, and spatial smoothing with an 8 mm Gaussian kernel. Then, for each subject, the nine contrasts (placebo, nocebo and control condition by pain anticipation, pain administration and pain rating) with the fixation (baseline) will each be calculated using a general linear model.

Group analysis will be performed using a random-effects model. A full factorial module in SPM 8 will be performed to test the differences between the inert Lidocaine, Capsaicin and control creams during pain anticipation, application and intensity ratings separately within each group; then we will compare the differences (between the Lidocaine and control, and Capsaicin and control) among the three groups (tDCS inhibition, tDCS enhancement and sham tDCS) to investigate how tDCS can modulate the placebo and nocebo effects. Covariates including LOT, ERS, STAI scores, gender, and experimenter effect will also be included in the model.

In addition, a multiple regression analysis will be performed between the placebo and nocebo effects as indicated by subjective pain rating differences and corresponding fMRI signal differences by pooling the data of all three groups (group indicator will be included in the model as a covariate). Covariates will include LOT, ERS, STAI scores, gender, and experimenter effect. As in previous studies [2, 4-6], a threshold of voxel-wise $p < 0.005$ with 20 contiguous voxels will be used for pre-defined ROIs. For non-ROI, a threshold of voxel-wise $p < 0.005$ and cluster level $p < 0.05$ Family-wise Error (FWE) corrected will be used.

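### Would the Aim 1 rating–signal regression cancel in the insula because a decrease is predicted there under both creams?

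*Protocol*

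**What the plan says.** Protocol, Specific Aims, Hypothesis 1.1 states that "placebo lidocaine and capsaicin will produce a significant pain rating decrease (placebo) and increase (nocebo) respectively", each against a within-subject neutral cream. Hypothesis 1.2 predicts, under placebo, "fMRI signal decreases in pain intensity sensitive regions (insula and secondary somatosensory cortex, S2"). Hypothesis 1.3 predicts, under nocebo, signal increases in other regions "along with fMRI signal decreases in the areas associated with the affective component of pain (dorsal anterior cingulated cortex (dACC) and insula"). No reason is given for the insula moving the same way while the ratings move in opposite ways.

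SAP, Specific Aim 1, first plans a factorial analysis of the three creams within each group. It then compares the lidocaine–control and capsaicin–control differences among the three tDCS groups. After that comes a further analysis: "a multiple regression analysis will be performed between the placebo and nocebo effects as indicated by subjective pain rating differences and corresponding fMRI signal differences". The three tDCS groups are pooled with a group indicator, and "Covariates will include LOT, ERS, STAI scores, gender, and experimenter effect". The text does not state the number of models, whether slopes are cream-specific, or how the differences are signed.

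On the rating scale, Session 1 of the Protocol trains subjects on the sensory scale, while for Session 2 it says "The Gracely Sensory and Affective Scale will be used to rate experienced pain during the stimulation afterward". The SAP does not name the scale used for the rating differences.

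**The concern.** With differences taken as cream minus control, the hypotheses give rating changes of (−, +) for (lidocaine, capsaicin) and insula changes of (−, −). If subjects with larger rating effects also have larger signal changes, the rating–insula slope is positive for lidocaine and negative for capsaicin. A single slope fitted to both creams would average the two. A real relation under each cream could then be reported as weak or absent, and an unexplained sign in Hypothesis 1.3 would appear to decide whether the analysis could find anything. The SAP names placebo and nocebo effects together in one sentence and lists no cream term or interaction, so a shared slope is not excluded outright.

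**Working it through.** The documents give no slope, standard deviation, correlation or power for this regression, so there is no stated figure to reproduce. The check has two parts: what a shared slope would do, and whether the SAP describes one.

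**Inputs from the documents.** Three groups of 26, so N = 3 × 26 = 78. The ROI threshold is voxel-wise p < 0.005 with 20 contiguous voxels. Directions are those of Hypotheses 1.1 to 1.3.

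**Assumptions.** Two-sided test of a single voxel or ROI mean, ignoring the 20-voxel rule. Covariates use 8 degrees of freedom (2 for group, about 6 for the rest). Partial correlation within each cream r = 0.30 to 0.50.

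**1. One regression per cream.** Residual df = 78 − 1 (intercept) − 1 (slope) − 8 = 68. The two-sided critical t at 0.005 is 2.90. The noncentrality is r/√(1 − r²) × √68.

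| r | noncentrality | power per cream |
|---|---|---|
| 0.30 | 2.59 | 39% |
| 0.35 | 3.08 | 57% |
| 0.40 | 3.60 | 75% |
| 0.50 | 4.76 | 97% |

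The test is two-sided, so the sign of the slope does not matter.

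**2. One shared slope on signed differences.** With a cream intercept and equal spread of ratings, the shared slope is about (lidocaine slope + capsaicin slope)/2. Take an assumed insula fall of 0.4 units per point of placebo effect, which is a slope of +0.4:

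- capsaicin slope −0.4: (0.4 − 0.4)/2 = 0
- capsaicin slope −0.3: (0.4 − 0.3)/2 = 0.05
- capsaicin slope −0.2: (0.4 − 0.2)/2 = 0.10
- capsaicin slope −0.1: (0.4 − 0.1)/2 = 0.15

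A simulation of 1,500 runs (assumed mean rating effects of 2 points, between-subject SD 1.5, residual SD 1.0) gave shared slopes of 0.00, 0.05, 0.10 and 0.15. Rejection was 1.3%, 4%, 19% and 49% with a cream intercept, and 0.5%, 10%, 54% and 95% without one. Separate regressions recovered each cream's own slope; in the equal case each was detected in about 98% of runs. Cancellation is therefore complete only when the two effects are equal in size. Otherwise the shared slope is attenuated, by an amount the documents do not fix.

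**3. Coding.** If ratings are coded as effect magnitudes and the signal stays as cream minus control, the hypotheses as written do not cancel: the equal case gives −0.40, detected in about 100% of runs. So even a shared slope does harm only under one of the possible codings.

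**4. What the SAP describes.**

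- The sentence before the regression defines the differences as two: lidocaine against control, and capsaicin against control.
- The regression pairs rating effects with corresponding signal differences, so each effect goes with its own contrast.
- The only pooling named is over the three tDCS groups. Pooling over creams is never mentioned.
- The listed terms are group, subject characteristics and experimenter. Stacking two rows per subject would call for a cream term or a subject term; their absence fits one row per subject in each regression.
- SAP, Specific Aim 2 uses the same phrase about placebo and nocebo effects for resting-state connectivity after the third tDCS. That measure has one value per subject and none per cream, so the phrase by itself does not imply stacked creams with a common slope.

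**5. Is the Hypothesis 1.3 sign the cause?** No. Hypothesis 1.2 predicts "fMRI signal increases in regions associated with the DPMS including the DLPFC, orbital prefrontal cortex (OPFC"), and Hypothesis 1.3 also predicts increases in DLPFC and OPFC. A shared signed slope would offset there as well, whatever the insula did. Changing or explaining the insula sign would not cure a shared slope, and separate slopes do not need it changed.

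**The case for a change.** The strongest reply is that an ambiguous sentence is itself a defect, that one more sentence would settle it, and that the loss under the wrong reading is not confined to exactly equal effects. In a further simulation at r = 0.35 with a cream term, a capsaicin slope of 75%, 50% or 25% of the lidocaine slope left the shared model with power of 1.4%, 3.9% or 11%, against 57% for the separate lidocaine regression. That is a real loss, and it stands as a statement about the shared model.

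It does not show that the SAP plans that model. Reaching the loss takes several steps the text does not contain: stacking the creams, forcing one slope, using signed coding, and carrying mean-level hypotheses over to subject-level slopes. Near-complete cancellation also needs effects of similar size. An analyst who stacked the creams would face two rows per subject and opposite-signed effects at once, and would have to add terms the SAP does not list.

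It is also true that the insula is called intensity-sensitive in one hypothesis and affective in the next, with no rationale, and that the rating scale is not named in the SAP. A line on each would help a reader. Neither alters the slope structure, and a decrease under both creams is not a contradiction: all three hypotheses can hold together.

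**Conclusion.** The observation about the wording is accurate, but no change to the plan follows. Read naturally, the SAP fits placebo and nocebo separately, and that analysis is sound whichever direction the insula takes: 39% to 97% power per cream for assumed r of 0.30 to 0.50 with 78 subjects at p < 0.005. A contrast between roughly 1% power under a shared slope and 74% or more under another sign is not a fair measure of risk. It compares versions of a model the SAP does not describe, at equal effect sizes, with r of at least 0.30, and with a cream term the SAP does not list.

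The regression is an addition to the factorial contrasts and group comparisons, which fit the creams separately, state no direction and are unaffected. The conclusion rests on the reading of the SAP set out above. It would change only if the analysts in fact fitted one common slope to signed differences from both creams.

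### Each cream's forearm row is randomised per subject but is not in any SAP model, so differences between skin sites stay in the error of every cream-minus-neutral contrast; this costs precision, by an unknown amount, and adding row is cheap

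*Protocol*

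**What the plan says.** **Layout (Protocol, Detailed experimental procedure, Session 2).** A 3x3 grid of 2 cm squares is drawn on the right volar forearm, "starting the grid at the subject's elbow crease". The creams are applied with "each cream spread onto a unique set of 3 adjacent squares (i.e. one cream for each row". Two creams therefore never share a row.

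**Allocation (same section).** "The row placement of the neutral control cream, placebo Lidocaine and Capsaicin creams will be randomized between subjects". A later sentence gives the purpose: "The location of the placebo, nocebo and control rows will be randomized across subjects to balance the experimental design". The method of randomisation is not described: nothing is said about blocking or about stratifying by tDCS group.

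**Test session (Session 5).** Lidocaine and capsaicin go back to their Session 2 positions ("cream administered to the same rows as determined in Session 2"). After the lateral column has been used, "we will administer the same moderate stimulus to all remaining regions with all 3 creams".

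**Analysis (SAP, Specific Aim 1).** The key comparison is that "we will compare the differences (between the Lidocaine and control, and Capsaicin and control) among the three groups". On adjustment: "Covariates including LOT, ERS, STAI scores, gender, and experimenter effect will also be included in the model". The Aim 1 and Aim 2 regressions that use the rating differences name the same covariates. Row, site and placement order appear nowhere in the SAP. Pain-rating difference is a primary outcome, but no model is given for comparing it between groups.

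**The concern.** The heat levels are chosen once per subject in Session 1; no calibration by row is described. If the rows differ in heat sensitivity, the same moderate stimulus will be felt differently under two creams for reasons unrelated to expectancy or tDCS. That difference goes directly into the subject's placebo or nocebo score. It does not average out within a subject, because all the squares tested for one cream lie in the same row and the row is fixed across sessions.

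The trial assigns this factor itself and so can know it for every subject. Left out of the model, its contribution stays in the residual, where it widens the confidence intervals for the placebo and nocebo effects and for their comparison among the three tDCS groups. With 26 per group there is little precision to spare.

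**Working it through.** **There is no plan figure to reproduce.** The documents give 26 per group without an effect size, SD, power or alpha for the ratings. The size of the problem can only be shown over a range of assumptions.

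**Inputs**
- From the protocol: 3 groups of 26; Gracely scale 0-20; three rows; one cream per row.
- Assumed: row effects of -a, 0 and +a Gracely points; residual SD of a subject's cream-minus-neutral difference (2 or 3 points); true difference between two tDCS groups of 0.79 residual SDs; two-sided 5% test; unrestricted randomisation of row order.

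**Step 1: variance added by row.** For one subject, D = cream effect + (row effect of active cream - row effect of neutral) + error. Of the 6 equally likely orders, 4 place the two creams in adjacent rows (squared difference a²) and 2 place them in the outer rows (squared difference 4a²). Hence

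Var(row difference) = (4/6)a² + (2/6)(4a²) = 2a².

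**Step 2: share of the total variance, 2a²/(SD² + 2a²)**

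| a | 2a² | share at SD 2 | share at SD 3 |
|---|---|---|---|
| 0.25 | 0.125 | 3% | 1% |
| 0.5 | 0.5 | 11% | 5% |
| 1 | 2 | 33% | 18% |

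**Step 3: power by hand for SD 2, a = 1.** The effect is 0.79 x 2 = 1.58 points. Without row, total SD = √(4 + 2) = 2.449, SE of the group difference = 2.449 x √(2/26) = 0.679, and 1.58/0.679 - 1.96 = 0.37, so power is about 64%. With the row variance removed, SE = 2 x √(2/26) = 0.555 and 1.58/0.555 - 1.96 = 0.89, so power is about 81% by the normal approximation.

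**Step 4: simulation.** 4,000 trials per cell with 3 x 26 subjects, analysed by least squares on D, with and without two row-difference terms. Each figure carries a simulation SE of about 0.6 points (√(0.8 x 0.2/4000)).

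| SD | a | power without row | power with row |
|---|---|---|---|
| 2 | 0 | 80% | 79% |
| 2 | 0.25 | 79% | 80% |
| 2 | 0.5 | 76% | 81% |
| 2 | 1 | 64% | 80% |
| 3 | 0.5 | 78% | 79% |
| 3 | 1 | 72% | 79% |

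Type I error was close to 5% with and without row.

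**Step 5: the same loss in subjects.** At SD 2, the number per group needed without row to match 26 with row is 26 x (1 + 2a²/4), rounded up: 27 at a = 0.25, 30 at a = 0.5 and 39 at a = 1.

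**Step 6: if row order was balanced within groups.** With orders spread as evenly as 26 allows in each group, at SD 2 and a = 1, power was still about 65% without row and 80% with it. The unadjusted test became conservative, with type I error just under 2%. Balancing the orders without modelling them leaves the row variance in the error term, so row belongs in the model under either scheme.

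**The case against.** **The plan already deals with row by randomising it.** This stands as far as bias is concerned. A reader might infer that the contrasts or the group comparison are biased; they are not. Randomisation makes the expected row difference zero, and the simulated type I error stays near 5%. It does not remove the row variance.

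**The row effect may be tiny.** This also stands. The centres of the outer rows are 4 cm apart on one forearm, and a = 1 means a gap of 2 Gracely points between them. The calibrated step from mild (5-6) to moderate (10-11) is only about 5 points. Nothing in the documents shows a gap that large. At a = 0.25 there is practically nothing to gain.

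**The covariate list may be open.** The Aim 1 list is introduced as non-exhaustive, and the rating model is missing altogether, so row has not been expressly excluded. That is fair, but nothing commits the analysis to include it.

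**Two stronger readings are tempting and should not be adopted.**
- *Unavoidable imbalance between tDCS groups.* One might argue that row was randomised without restriction and that 26 does not divide by 6. The documents do not say that randomisation was unrestricted, and the stated aim is balance. All three groups could have the same order counts (for example 5, 5, 4, 4, 4, 4), which balances them exactly against each other.
- *Chance imbalance as a second harm on top of lost precision.* Under unrestricted randomisation, chance imbalance is the same 2a² component divided by the group size. It is already inside the power figures, and counting it again would be double counting.

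**Conclusion.** The point holds as a matter of precision. Row is a design factor that the trial randomises and can know, it differs between the two creams in every contrast, and no SAP model names it. The loss ranges from nothing at a of 0.25 or less, through roughly 1 to 5 points of power at a = 0.5, to roughly 7 to 16 points at a = 1, for residual SDs of 3 and 2 respectively. The row effect, the residual SD and the 0.79 SD target are all assumptions. The figures concern pain ratings; the same argument applies to the fMRI contrasts, but the documents allow no size to be put on it there.

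This is a cheap improvement. It does not threaten the validity of the trial. Fixed row terms remove only the average row effect; variation in site sensitivity peculiar to a subject would remain.

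**What to change.** Add to the SAP:

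- **Pain ratings (Aim 1).** When the missing group-comparison model is written, include row (three levels, 2 df) as a within-subject fixed effect alongside cream, tDCS group and their interaction.
- **fMRI group analyses (Aim 1).** For the lidocaine-minus-neutral and capsaicin-minus-neutral images, add two row-difference covariates. Each is the indicator that the active cream is in a given row minus the same indicator for the neutral cream, for two of the three rows.
- **Regressions that use the rating differences (Aims 1 and 2).** Add the same two covariates.

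State how the row order was generated, and keep it in the analysis data set.

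The cost is a sentence or two in the SAP and 2 df per model. If there is no row effect, about one point of power is lost. No new measurement is needed, because the trial itself assigns the rows.
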